9.3.1 Primary Endpoint Analysis

Frequencies, percentages and two-sided exact 95% confidence intervals will be calculated for the three primary endpoints for the entire study population and for selected subgroups.

9.3.1.1 A: Actual Use: Proportion of dosing instances among user population taken within 120 hours (5 days) of most recent episode of unprotected sex.

The first primary endpoint is the proportion in which the denominator includes all dosing instances of the IP and the numerator includes all dosing instances of the IP which were taken within 120 hours (5 days) of the subject's most recent episode of unprotected sex.

9.3.1.2 B: Actual Use: Proportion of dosing instances among user population in which no more than one tablet was taken.

The second primary endpoint is the proportion in which the denominator is all discrete dosing instances of the IP and the numerator includes all dosing instances where no more than one tablet was taken.

9.3.1.3 C: Self-Selection: Proportion of female selectors who are not pregnant at the time of selection decision.

The third primary endpoint is the proportion in which the denominator includes all females who selected to use the product (regardless of whether they purchased/used) and the numerator includes all female selectors who were not pregnant at the time of the selection decision. In the case of subjects that report not being pregnant, sign consent and then receive a positive result on the pregnancy test, the second selection decision will be used for analysis of this endpoint.

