Rationale: The Sponsor proposes to test this message as a primary endpoint as it would allow the study to confirm that consumers do not select or take ella® if they are already pregnant, although the available safety data are reassuring for pregnant women exposed to ella®.

Secondary

D	Self-Selection: Proportion of female selectors who are not breastfeeding at the time of selection decision.	Warnings: Do not use if you are breastfeeding
---	---	---

Rationale: While it has been shown that UPA and its metabolite are both excreted in breastmilk over the first 120 hours after administration, UPA is unlikely to have any detrimental effects on the newborn infant if ingested in breast milk, given the mechanism of action of UPA and the fact that there is no role for progesterone in the newborn infant. To date, no safety signal has been identified in newborns breastfed by women who have taken UPA 30mg.

Because breastfeeding is not a contraindication for use of ella® in the prescription setting (though it is not recommended because of a lack of clinical data), this has been designated as a secondary endpoint in this AUT.

E	Self-Selection: Proportion of self-selection population who make a correct	• Do not use if you are already pregnant
---	--	--

selection decision.	
• Do not use for regular birth control• Do not use more than once in the same menstrual cycle• Do not use if you are breastfeeding• Use: for women to reduce chance of pregnancy after unprotected sex• Allergy alert: Do not use if you have ever had an allergic reaction to any of the ingredients
---------------------	---

Rationale: The main goal of the AUT is to assess actual use of ella®. Given that potential clinical consequence of incorrect selection is unlikely to be serious, the Sponsor proposes to test correct self-selection of potential consumers as a secondary endpoint.

F	Actual Use: Proportion of dosing instances among user population in which HBC is not taken for 5 days after taking ella®.	Directions: After taking this product; users of birth control pills, patch or vaginal ring after use of this product: Do not use birth control pills, patch or vaginal ring for 5 days after taking this product. If you do, it may block the ability of both this product and your birth control to work.
---	---	--

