3.3.2 Exclusion Criteria: Use Phase

All subjects who agree to participate at the site will be asked to make a selection decision. Subjects presenting with any of the following will not be included in the use phase of the study (i.e., will not be allowed to purchase and use study medication):

1. Unwilling to purchase study medication.
2. Unwilling to provide written informed consent.
3. Unwilling or unable to provide contact information.
4. Unwilling to state that the product is for their own use and no one else's.
5. Pregnant, by self-report or by a urine pregnancy test.
6. Male.
7. Known allergy to ulipristal acetate or inactive ingredients.
8. Currently breastfeeding.
9. Premenarchal (have not experienced a first menstrual cycle).

Subject eligibility will be reviewed and documented by the Investigator or his/her designee before subjects are allowed to purchase and begin the use phase of the study.

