8.4.1 Selection Decision

The selection phase of the interview consists of the self-selection question and the purchase question, with accompanying neutral follow-up questions. All subjects who go on to actually purchase the study product will be categorized as selectors. Even subjects who do not eventually complete the purchase of the product will be classified as a selector or a non-selector on the basis of the initial selection and purchase questions. However, all information recorded during the selection phase of the interview will be considered in the classification of subjects as selectors or non-selectors. Subjects who offer modifying information in open-ended responses to neutral probing will be re-

categorized accordingly. Please note that for this study, subjects are offered the opportunity to enroll when they present for purchase of EC. That is, these are subjects who came to the site having already determined they need EC and expecting to purchase EC.

A subject who initially indicates that they would select and purchase the product, but who independently and unprompted changes their purchase decision during the selection phase of the interview would be categorized as a non-selector. For the majority of subjects, any information offered once the interview proceeds beyond the selection phase of the interview will not be considered during selection classification. However, for subjects that self-report not being pregnant, sign consent and then receive a positive result from the enrollment pregnancy test, the selection questions will be asked again and used to classify the subject as a selector or non-selector. Financial and cost-related reasons for saying no to the purchase question will not be used as rationale for re-classifying subjects who would otherwise be selectors.

The selection decision for each subject will be examined on a case-by-case basis, taking into account all the information gathered during the selection phase of the interview. Two independent coders will evaluate the available data and indicate whether the subject is a selector or a non-selector. Discrepancies will be resolved by a third coder (as described in Section 8.4.3).

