9.1 Sample Size Determination

For the purposes of this AUT, sample size has been set for practical and logistical reasons at approximately 950 purchasers. Given that subjects are recruited after independently seeking EC, most of those who enter the self-selection phase are expected to purchase, and most purchasers are expected to actually use the product during the study. If approximately 75% of subjects pass the screening criteria, self-select

and both qualify and agree to purchase and enter the use phase, it is expected that up to 1270 subjects will need to be interviewed to yield 950 purchasers.

Assuming approximately 950 purchasers, if 80% of those purchasers use the product within the study period, that would yield a user population of 760. Estimating approximately 40% of users will have had recent hormonal contraceptive use would yield a recent hormonal contraceptive users population of 305. Allowing for a further 20% loss to follow-up yields a user population of approximately 608 and a recent hormonal contraceptive user population of 245.

Because actual use trials are not hypothesis-testing comparative trials, study sample size is designed to allow for adequate evaluation of key endpoints across all subjects and among several subgroups. As the analysis of actual use trials typically focuses on estimating the proportion (and associated 95% confidence intervals) of individual endpoints, sample size is most often based on the number of subjects needed to constrain the confidence interval (CI) to a limited range. For this study, assuming 85% correct response (the confidence interval depends on the actual point estimate), a sample of 608 subjects would constrain the CI to $\pm 3.1\%$. For purposes of illustration, Table 5 provides the 2-sided exact 95% confidence interval for various sample sizes around a point estimate of 85%.

Table 5 Two-sided 95% CIs for Various Sample Sizes Around 85% Point Estimate

	N=760 ^a	N=608 ^b	N=245 ^c	N=143 ^d
95% CI around a point estimate of 85%	$\pm 2.7\%$	$\pm 3.1\%$	$\pm 5.1\%$	$\pm 7.0\%$

^a User population (maximum)

^b User population (allowing for loss-to-follow up)

^c Recent hormonal contraceptive users

^d Low literacy subjects

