9.3 Endpoint Analysis

A summary of the disposition of subjects (including responders, self-selection population, purchasers and users) and reasons for exclusion from these populations will be provided. Demographic characteristics, medical history and other background information will be summarized for the responder, self-selection, purchaser, and user populations.

Frequencies and percentages will be presented for categorical data, mean, standard deviation (SD); median, and range will be presented for numerical data.

Frequencies, percentages and 2-sided 95% CI will be calculated for the primary and secondary endpoints using the exact method. For the primary endpoints, it will be concluded that the established target threshold is reached if the lower limit of the CI of the point estimate is equal to or exceeds the value of the pre-determined threshold.

Several of the endpoints are based on dosing instance, rather than by subject, as subjects have the potential to take more than one dose over the course of the study. Correctness of selection or behavior can only be evaluated at the time of use, rather than at the time of purchase. However, for each of those endpoints a secondary analysis by subject will also be presented.

Endpoints and demographics will be presented for subgroups of interest, with subjects dichotomized on the corresponding variables, which include (but are not necessarily limited to) literacy, gender, age (adolescent vs. adult women), and history of HBC use.

A more detailed description of planned data analysis procedures will be found in the SAP which will be approved and signed before the database is locked.

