The Sponsor proposes to test this message as a primary endpoint as it would allow the study to confirm that consumers do not select ella® if they know they are already pregnant.

Of important note, the caution against use if already pregnant is on the approved and marketed PBOS DFL that uses the exact same language as that proposed on the ella® DFL (“Do not use if you are already pregnant (because it will not work)”. The ella® LCS demonstrated that consumers understand this warning extremely well. Moreover, data suggest use of ella® in pregnancy is safe. For ella®, the analysis of the global pregnancy safety database conducted in the context of the Ellipse II study has been specifically intended to assess the occurrence rates of outcomes of pregnancies exposed to ella® due either to failure of the EC or inadvertent exposure during pregnancy, including fetal and neonatal outcomes and maternal pregnancy complications. Data from the collected UPA-exposed pregnancies did not reveal a negative signal on the course of the pregnancy, its outcome, or the growth and development of the embryo and the fetus.

Despite the fact that the available safety data are reassuring were a pregnant woman to take ella®, this has been designated as a primary endpoint in this AUT with a 90% threshold.

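### Primary endpoint C gives the share of selectors who are not pregnant, so a pass cannot confirm, as Protocol 2.3 and 9.3.2 say, that pregnant women do not select

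*Protocol*

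**What the plan says.** Section 9.3.1.3 defines primary endpoint C. The denominator is every female who selected the product, whether or not she bought or used it, and "the numerator includes all female selectors who were not pregnant at the time of the selection decision". For a woman who reports not being pregnant and then tests positive, "the second selection decision will be used for analysis of this endpoint". Section 9.3.2 sets the pass rule: the lower limit of the two-sided exact 95% interval must be at least 90%.

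Two sections state what C is for. The rationale in section 2.3 (Table 1) says "it would allow the study to confirm that consumers do not select or take" the product if they are already pregnant. Section 9.3.2 says it would confirm that consumers do not select the product "if they know they are already pregnant".

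Section 3.3.2 bars from the use phase anyone who is "Pregnant, by self-report or by a urine pregnancy test". Section 9.3.3.2.2 expects very few subjects to be inappropriate for use. It also offers, under secondary endpoint E, the ratio D/(B+D): the share of those who should not select who correctly do not.

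**The concern.** The definition and the stated aims condition on different groups. C starts from selectors and asks how many are not pregnant. The aims start from pregnant women and ask whether they decline. The women whose behaviour would show that the warning works, those who are pregnant and decline, are absent from both counts of C.

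C is one of three primary endpoints with a pass rule in a study that section 1 calls pivotal. A reader of 2.3 or 9.3.2 would take a pass as evidence that the pregnancy warning is heeded. If few pregnant women present, the pass says almost nothing on that.

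The words about taking the product in 2.3 go further still. C is fixed at the selection decision, and women found pregnant at enrollment never receive the product, so C holds no information on use by them.

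**Working it through.** **Inputs.** Definition of C: 9.3.1.3. Exact two-sided 95% interval and 90% rule: 9.3.1 and 9.3.2. Scale: about 950 purchasers, and "up to 1270 subjects will need to be interviewed to yield 950 purchasers" (9.1). Pregnancy prevalence: not given, so a range is assumed.

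**The plan's own figures.** The protocol states no precision for C. Its Table 5 (section 9.1) was used to check the interval method. The Clopper-Pearson distance from estimate to lower limit is 2.74 points for 646/760, 3.09 for 517/608, 5.11 for 208/245 and 6.98 for 121/143. These match the stated 2.7, 3.1, 5.1 and 7.0. Also 950/0.75 = 1,267, which matches up to 1,270.

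**Formula.** Let m be the non-pregnant female selectors, g the pregnant women who make a decision, and d the share of them who decline. The aims concern d. The endpoint is

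C = m / [m + g(1 − d)].

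When g is small beside m, C is close to 1 whatever d is.

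**How many pregnant selectors C tolerates.** Take d = 0 and let N be all women who would select if no pregnant woman declined.

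- N = 950: 76 pregnant (8.0%) gives 874/950, lower limit 90.09%, a pass. With 77 the limit is 89.97%, a fail.
- N = 1,270, a ceiling because it counts interviews: 105 pregnant (8.3%) gives 90.08%, a pass. With 106 the limit is 89.99%, a fail.
- 950 taken as the non-pregnant selectors instead of the total: 84 pregnant gives 950/1,034 (8.1% pregnant), lower limit 90.04%, a pass. With 85 the limit is 89.95%, a fail.

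The limit is about 8% on each base.

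**Effect of behaviour on C, N = 950.**

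| Assumed pregnant | Declining | C | Lower limit | 90% rule |
|---|---|---|---|---|
| 10 (1%) | none | 940/950 = 98.95% | 98.07% | met |
| 10 (1%) | half | 940/945 = 99.47% | 98.77% | met |
| 48 (5%) | none | 902/950 = 94.95% | 93.36% | met |
| 48 (5%) | half | 902/926 = 97.41% | 96.17% | met |
| 48 (5%) | all | 902/902 = 100% | 99.59% | met |
| 76 (8%) | none | 874/950 = 92.0% | 90.09% | met |
| 95 (10%) | none | 855/950 = 90.0% | 87.91% | not met |

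Allowing for sampling, the chance of passing with N = 950 and no pregnant woman declining is above 0.999 at a true prevalence of 5%, 0.90 at 7% and 0.53 at 8%.

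**Could the 90% rule move to d?** If all g pregnant women decline, the exact lower limit is 0.025^(1/g). That is 69.2% for g = 10, 82.4% for g = 19 and 90.3% for g = 36; with g = 35 it falls just short at 89.997%. At least 36 pregnant women, all declining, would be needed.

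**Does another planned figure supply d?** D/(B+D) pools pregnancy with breastfeeding, allergy, male sex, lack of childbearing potential and no recent unprotected sex. By 8.4.2 and 9.3.3.2.1, cell D also takes in otherwise eligible women who give a medical reason for declining. Section 9.3 promises that "reasons for exclusion from these populations will be provided", but exclusion counts are not selection decisions.

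**The case against.** The best defence is that C is a sound quantity in its own right. The share of pregnant women among selectors describes exposure in an over-the-counter setting, and C bounds it correctly. This stands, and C should stay. A measure conditional on pregnancy could not carry a 90% rule in a study expecting few such women. This also stands, and it is why none is proposed. The protocol does not rest the warning on C alone either, since 9.3.2 also cites the label comprehension study.

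It may be said that descriptive breakdowns belong in the statistical analysis plan. That does not answer the point: the definition, the threshold and the inference claimed from them are all fixed in this protocol, and they do not match.

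Two stronger readings are tempting, and the documents do not support them.

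- A reader might infer that recruiting to about 950 purchasers inflates C, because "All subjects who go on to actually purchase the study product will be categorized as selectors" and none may be pregnant. But the denominator counts selectors regardless of purchase, and 8.4.2 classes pregnant women who select as incorrect selectors although they cannot buy. They accrue alongside purchasers, so the recruitment target does not tilt the ratio.
- A reader might infer that using the second decision after a positive test biases C. The rule fits the aim in 9.3.2 about women who know they are pregnant. It is also stricter than self-report alone, under which such a woman would count as a success; here she becomes a failure or drops out. At 1% to 5% pregnant it cannot change the verdict.

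**Conclusion.** The concern holds. A pass on C shows that the upper 95% limit for the pregnant share of female selectors is no more than 10%. It does not show that pregnant women decline, and it cannot speak to whether they take the product.

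The size depends on a prevalence that the documents do not give. Below about 8% pregnant among women who would select, the observed C meets the rule even if nobody heeds the warning. The protocol's expectation of very few inappropriate subjects points to that region but does not prove it. A pass is not guaranteed: at 10% pregnant with none declining, C fails. The fault lies in the conclusion attached to C; its calculation and threshold are not in question.

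**What to change.** 1. Keep C and its threshold. State its conclusion as the share of female selectors who are pregnant.
2. Reword the rationales in 2.3 and 9.3.2 to match. Remove the reference to taking the product from 2.3, and align 2.3 with the wording in 9.3.2 about women who know they are pregnant.
3. Report descriptively, with exact interval and no threshold, the proportion of women self-reporting pregnancy at enrollment who did not select. If there are none, state that the warning was not tested.
4. For pregnancies found by the urine test, give only counts of the first and second decisions.

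The cost is wording in two sections and one table. No new data are needed: section 6.6 has all subjects asked about pregnancy, and the selection question is already put again after a positive test. The drawback is that the self-reported pregnant group may be very small or empty, so the interval will be wide: 9 of 10 not selecting would give 55.5% to 99.7%.

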9.3.2 Target Thresholds

The threshold for the three primary endpoints is 90%. The objective will be considered met for these endpoints if the lower bound of the 2-sided 95% CI for each endpoint meets or exceeds the established threshold.

- *A: Actual use: Proportion of dosing instances among user population taken within 120 hours (5 days) of most recent episode of unprotected sex.*

The Sponsor proposes to test this message as a primary endpoint because it communicates directions for effective use of ella®, and the limited time-window for its effective use. Use of ella® after 5 days diminishes or abolishes the product's efficacy, although it is not expected to introduce any drug-related risks. Despite the fact that this label language is almost identical to the label language tested, approved, and in-market for Plan B One-Step (PBOS) (which is "Take as soon as possible and no later than 3 days (72 hours) after unprotected sex"), the Sponsor will test this as a primary endpoint.

Testing it as a primary endpoint would test whether the longer time window (5 vs 3 days) during which consumers may benefit from ella® use is well-followed. This would also allow us to confirm that consumers do not take ella® later after unprotected intercourse than recommended in the product label.

A performance threshold of 90% is proposed because while taking the product within the 5-day window is very important to maximize effectiveness, taking it outside of the 5 days window is not expected to introduce any serious drug-related risks.

- *B: Actual Use: Proportion of dosing instances among user population in which no more than one tablet was taken.*

The Sponsor proposes to test this message as a primary endpoint in the context of FDA's recommendation to demonstrate in an AUT whether consumers misuse ella® and one of the potential misuse scenarios would be the intake of more than the recommended dose, which would be assessed through this endpoint.

A threshold of 90% was designated despite the fact that dose-finding studies using up to 200 mg of UPA (more than 6 times the intended 30 mg dose) demonstrated no safety concerns (HRA2914-503). Accordingly, it is likely that taking more than the recommended dose is likely to impose little or no additional risk in women.

- *C: Self-Selection: Proportion of female selectors who are not pregnant at the time of selection decision.*

The Sponsor proposes to test this message as a primary endpoint as it would allow the study to confirm that consumers do not select ella® if they know they are already pregnant.

Of important note, the caution against use if already pregnant is on the approved and marketed PBOS DFL that uses the exact same language as that proposed on the ella® DFL (“Do not use if you are already pregnant (because it will not work)”. The ella® LCS demonstrated that consumers understand this warning extremely well. Moreover, data suggest use of ella® in pregnancy is safe. For ella®, the analysis of the global pregnancy safety database conducted in the context of the Ellipse II study has been specifically intended to assess the occurrence rates of outcomes of pregnancies exposed to ella® due either to failure of the EC or inadvertent exposure during pregnancy, including fetal and neonatal outcomes and maternal pregnancy complications. Data from the collected UPA-exposed pregnancies did not reveal a negative signal on the course of the pregnancy, its outcome, or the growth and development of the embryo and the fetus.

Despite the fact that the available safety data are reassuring were a pregnant woman to take ella®, this has been designated as a primary endpoint in this AUT with a 90% threshold.

